PROTOCOL FOR RESEARCH INVOLVING HUMAN SUBJECTS

**TITLE OF PROJECT: Cervical Spondylotic Myelopathy Surgical Trial (CSM-S Trial)
VERSION: 6.0, DATE: 12-17-24**

Study Sponsor: Patient-Centered Outcomes Research Institute (PCORI) & Alan and Jackie Stuart Spine Research Center

	Name	Signature	Email Address
Principal Investigator:	[name] MD		[contact]
Other Investigator(s):			
Correspondent			

Mailing Address:

[name]
[name]

[contact]
[contact]

II. DESCRIPTION OF STUDY

A. Purpose

1a. To determine if ventral surgery is associated with superior SF-36 PCS outcome at one year follow-up compared to dorsal (fusion or laminoplasty) surgery.

1b. To determine if, compared to pre-operative baseline status, both ventral and dorsal surgery for CSM improve symptoms of spinal cord dysfunction using mJOA.

2. To determine if, from a patient perspective, health resource utilization (out-of-pocket expenses and loss of productivity) for ventral surgery, dorsal fusion, and laminoplasty surgery are different.

3. To determine if cervical sagittal balance post-operatively is a significant predictor of SF-36 PCS outcome.

B. Background

Surgical decompression for CSM can improve its disabling symptoms, but surgical complications are common and many of these complications affect patients' overall health-related quality of life. The optimal surgical treatment, therefore, remains controversial, with disagreement between three main approaches: ventral decompression and fusion, dorsal decompression and fusion, or dorsal laminoplasty. This study aims to test the hypothesis that ventral surgery is associated with superior SF-36 PCS outcome at one year follow-up compared to dorsal approaches and that both ventral and dorsal surgery improve symptoms of spinal cord dysfunction using the mJOA score. A secondary hypothesis is that health resource utilization for ventral surgery, dorsal fusion, and laminoplasty surgery are different. A third hypothesis is that cervical sagittal balance post-operatively is a significant predictor of SF-36 PCS outcome.

C. Specific Location of Study

This is a multi-center trial. Subjects will be entered into the study from 10 separate centers.

D. Probable Duration of Project

Subjects will be recruited into the study over an 18 month period. All subjects will be followed for 5 years with clinical questionnaires.

E. Research Plan

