flexion-extension radiographs will be obtained pre-operatively on all patients and at one year after surgery to assess cervical fusion and/ or radiographic complications. Standing cervical-thoracic-lumbar-sacral films will be obtained on all patients pre-operatively and at one year postoperatively (post-operatively in the randomized group only) to assess cervical as well as overall sagittal balance. A cervical spine CT will be obtained on patients at 1 year who have an NDI score > 30 or whose plain films suggest instability.

7) A study coordinator will collect data at 30 days and at 1 year to document any complications or re-operations. Additionally, the study coordinator will assess whether the patient is having any swallowing complications following surgery.

8) Health resource utilization information (including out-of-pocket expenses) will be obtained using patient diaries along with copies of all medical bills and receipts at 1 month, 3 months, 6 months, and 12 months post-operatively for all of the patients. Participants also will be asked to keep track of days missed from work and days unable to perform usual activities, in addition to days missed from work for medical treatments or evaluations.

F. Data and Safety Monitoring Plan

- 1) All serious unexpected adverse events (e.g. death within 30 days of operation) will be reported to the IRB within 24 hours. Any appropriate funding agencies or regulatory agencies would be notified as well.
- 2) Any serious anticipated adverse event (e.g. wound infection, pulmonary embolus) will be reported to the IRB whenever their magnitude or frequency exceeds expectations.
- 3) All other adverse events (including loss of privacy, significant economic harm) will be reported to the IRB on an annual basis or at the time that re-approval is sought. Any adverse event judged unlikely or unrelated to the study will also be included in an annual report for the IRB.

G. Statistical Considerations

a. Specific data variables being collected for the study.

The data collection sheets will be submitted along with this protocol. There will be several data sheets as follows:

- 1) Screening/Baseline, 1 Month, 3 Months, 6 Months, and 1 Year Visit Checklist
- 2) Informed Consent Process
- 3) Inclusion/Exclusion Criteria
- 4) Baseline Demographics
- 5) Spine surgeon's data sheet

- 6) 30-day and 1 Year morbidity data sheet
- 7) 1 Month, 3 Months, 6 Months, 1 Year Return to Work Status
- 8) 3 Month Swallowing Evaluation

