- 9) Initial Hospital Admission Data Sheet
- 10) 3 Months and 1 Year Radiology
- 11) End of Study
- 12) Adverse Event Form
- 13) Serious Adverse Event Report Form
- 14) Serious Adverse Event Follow-up Report Form
- 15) SF-36 questionnaires (pre-op, 3 months, 6 months, 1, 2, 3, 4, and 5 years),
- 16) Neck Disability Index questionnaires (pre-op, 3 months, 6 months, 1, 2, 3, 4, and 5 years)
- 17) mJOA, (pre-op, 3 months, 6 months, and 1 year)
- 18) EuroQol-5D (pre-op, 3 months, 6 months, 1, 2, 3, 4, and 5 years)
- 19) Health Resource Utilization Diary (1 month, 3 months, 6 months, 1 year)
- 20) Report of Second Cervical Surgery
- 21) Death Form
- 22) Inpatient Hospital and Rehabilitation Utilization Data Sheet
- 23) Long term follow-up phone questionnaire (2, 3, 4, and 5 years)

b. Study endpoints.

Subjects will be followed for 5 years. The primary endpoint will be the 1-year change in SF-36 physical component summary score (PCS) at one year. Secondary endpoints will include the 1-year change in mJOA, NDI, and EuroQol-5D scores as well as the observed complication rates, health service utilization, work status, and sagittal balance measurements.

c. Statistical Methods.

Primary analyses will include all subjects randomized using an intent-to-treat approach. The primary endpoint is the 1-year change in Physical Component Summary of the SF-36 (SF-36 PCS) at one year. A likelihood-based analysis using a mixed model will be used to compare SF-36 PCS between groups. This model will adjust for baseline SF-36 PCS, as well as study surgeon using a random effects model. All time points will be included in the model, and each subject will contribute data for the time points at which they were assessed. The model enables a statistical comparison between treatment groups at each time point, though the comparison at the one-year time point will be the primary analysis. The primary advantage of the mixed model, when compared to commonly used methods such as complete case analysis and single imputation (e.g. last observation carried forward), is its flexibility in handling missing data. This analysis will assume that missing data occurs at random (i.e. the missing data value can be dependent on observed data, but independent of unobserved

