The research team has extensive experience conducting economic evaluations, including assessment of musculoskeletal interventions alongside RCTs and will conduct the proposed patient-oriented health resource utilization analysis. We will collect health resource utilization data as well as health cost data alongside this RCT.

Cost Analysis

Costs will be estimated for each patient from a societal perspective from the sources listed below, including only patients from the United States. A one-year time horizon will be selected to align with the primary outcome measure of the CSM-S Trial.

A. Index Hospitalization Costs:

- Hospital Costs: Total hospital charges (TotalHC) will be used to estimate costs using hospital-specific and year-specific Medicare cost-to-charge ratios (CCR). The costs will be adjusted for inflation to the current year without a 3% discount.
 - As a sub-analysis, hospital charges for specific revenue-centers (i.e., radiology, pharmacy, physiotherapy and occupational therapy) will be converted to costs using hospital-specific and year-specific Medicare CCRs. This will allow the identification of the major drivers of the difference in cost between the surgical strategies. A crosswalk between the revenue center and the cost center will be created.
- For professional services (identified with either HCPCS code or CPT-4 codes) provided to patients during the index hospitalization, costs will be calculated using national reimbursement amounts from the appropriate Medicare fee schedules for the respective year and site.

B. One-Year All-Cause Costs:

- One-year total hospital charges will be utilized in this part of the analysis. These include major health resource utilization events in the year following surgery including readmission, reoperation, injections, advanced imaging, and physical therapy.
 - Year-specific, site-specific Medicare cost-to-charge ratios, will be used to determine one-year costs from charges. These costs will be inflation adjusted. Professional services will also be included (identified with either HCPCS code or CPT-4 codes) and costs will be calculated using national reimbursement amounts from the appropriate Medicare fee schedules for the respective year and site.

C. Costs Due to Lost Productivity:

- We will assume that work was halted for patients on the procedure date.

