- Lost wages will be estimated according to patients' occupations using the median weekly earnings in the US (for the current year) as reported by the Bureau of Labor Statistics.

- Lost wages for retirees will be valued at 65% of an employed patient and based on time to return to normal activities, which will be assumed to be three months

Hospitalization costs and one-year all-cause costs (total direct costs) will be combined with costs due to loss of productivity (indirect costs) to estimate total costs of each surgical procedure from a societal perspective.

Statistical Analysis Plan: The three cost outcomes will be reported in US Dollars and inflation-adjusted to the current year using the Gross Domestic Product Implicit Price Deflator. We will provide the descriptive statistics for the three outcomes (mean, median, standard deviation or SD, interquartile range, minimum, and maximum). Given that the cost outcomes are expected to follow a skewed distribution (non-normal), we will use generalized linear modeling (GLM) with Gamma distribution and a logarithmic link for cost. Any baseline patient characteristics found to be imbalanced between the cohorts will be adjusted for in the GLM. The mean predicted costs for each cohort and the differences in those predicted costs along with the 95% confidence intervals will be generated. If 10% or more of the overall study population has zero costs for the 1-year outcome, two-part modeling will be implemented. This will utilize a logistic regression to predict the presence of positive costs and a GLM model to predict non-zero costs as described above.

Calculation of Utility and Quality-Adjusted Life Years (QALY) Gained

- EQ-5D health-related quality-of-life questionnaires have been collected at baseline, 3 months, 6-months, 1-year, and 2-years. 1-year data will be used for cost-utility analyses.
 - For patients without complete data (i.e., without responses at all time points in the first year), we will assume missingness at random (MAR) and multiple imputation will be performed.
- Patient responses to the EQ-5D instrument will be mapped to utilities using the U.S. population value set and QALYs will be calculated for cost-utility analysis assuming a linear relationship between consecutive survey timepoints.

Incremental Cost-Effectiveness Ratio (ICER)

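### A fixed three-month recovery for every retiree prevents the cost analysis from showing recovery differences in that group, and Aim 2's out-of-pocket comparison has no stated analysis

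*Combined protocol and SAP*

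**What the plan says.** **Aim.** Aim 2 (II.A Purpose) asks whether the three procedures differ, "from a patient perspective, health resource utilization (out-of-pocket expenses and loss of productivity" being its two named components.

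**Data.** II.E Research Plan, item 8 states: "Health resource utilization information (including out-of-pocket expenses) will be obtained using patient diaries along with copies of all medical bills and receipts", at four visits up to 12 months. The same item adds: "Participants also will be asked to keep track of days missed from work and days unable to perform usual activities". The list of data sheets (II.G.a, item 19) has "Health Resource Utilization Diary (1 month, 3 months, 6 months, 1 year".

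**Endpoints.** II.G.b includes among the secondary endpoints "observed complication rates, health service utilization, work status, and sagittal balance measurements".

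**Analysis.** The introduction to the Analysis Plan for Cost-Effectiveness (II.G.c) says the team "will conduct the proposed patient-oriented health resource utilization analysis". The Cost Analysis section then sets a different perspective: "Costs will be estimated for each patient from a societal perspective from the sources listed below, including only patients from the United States". It takes a one-year horizon and three sources: index hospitalization (A), one-year all-cause costs (B) and lost productivity (C). Under C, retirees are valued at 65% of an employed patient, "based on time to return to normal activities, which will be assumed to be three months". No exception, procedure-specific value or sensitivity analysis of the three months is stated. The ICER section plans a probabilistic analysis for sampling variation.

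**The concern.** There are two gaps between what Aim 2 asks and what the cost section can deliver.

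First, loss of productivity is a component of the aim, and for retirees the quantity that could differ between procedures is how long normal life is interrupted. The plan replaces that quantity with a constant. If retirees recover at the same pace after all three operations, the constant introduces no difference that should not be there, but the analysis could not demonstrate the equality. If they do not, the difference is recorded as zero and its uncertainty is absent from the ICER. Eligibility runs from 45 to 80 years, so retirees may be a sizeable group; the documents do not give their share.

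Second, out-of-pocket expense is named in the aim and collected from all patients, yet no comparison of it is described. The specified method estimates societal cost, which answers a different question from what patients themselves pay.

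**Working it through.** The plan states no figure to reproduce here, so the check is the algebra of the rule followed by a comparison of sections.

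**1. What the rule assigns.** Inputs: weight 0.65 and three months (Cost Analysis, part C). Three months = 3 × 52/12 = 13 weeks. Let W be the reference weekly wage, for which the documents give no amount.
- Cost per retiree = 0.65 × 13 × W = 8.45 W, for every procedure.
- Recovery-time difference between any two procedures = 0.65 × (13 − 13) × W = 0.
- Variance contributed by recovery time = 0, because the duration is constant. Resampling patients can still vary the retired share and the wage, but not the duration.

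**2. What individual durations would give.** Each week of difference in mean recovery is worth 0.65 W per retiree. The following is hypothetical: the weeks and retired shares are assumed, the share and W are taken as equal across procedures, and only the retiree component is counted.
- 4 versus 8 weeks: 0.65 × 4 = 2.6 W per retiree
- 6 versus 13 weeks: 0.65 × 7 = 4.55 W per retiree
- 8 versus 26 weeks: 0.65 × 18 = 11.7 W per retiree
- 13 versus 13 weeks: 0

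With 20% to 60% retired, the three non-zero cases run from 0.20 × 2.6 = 0.52 W to 0.60 × 11.7 = 7.02 W per patient. The plan records 0 in each. These figures show how the rule behaves; they do not estimate or bound the effect in this trial.

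**3. Whether an imbalance in retired share gives a signed bias.** Suppose one procedure has 10 percentage points more retirees. The retiree component alone rises by 0.10 × 8.45 = 0.845 W per patient. If those retirees stand in place of employed patients who are off work for 13 weeks, the net change is 0.10 × (8.45 − 13) = −0.455 W. The sign depends on who is replaced and for how long they were off work, so no direction follows.

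**4. Whether individual information is requested.** Item 8 asks for days lost to usual activities. The utilization diary is scheduled to one year, matching the cost horizon and running past the three months assumed. However, no listed form names a field for these days, and no completeness figure is given. A count of such days is also only a proxy: bad days can be intermittent, whereas part C refers to elapsed time until normal activity resumes.

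**5. Out-of-pocket expense, traced through the plan.** It is named in Aim 2 and collected under item 8. It is then absent from the cost section, whose components are hospital charges converted by cost-to-charge ratios, professional services at Medicare fee-schedule amounts, and lost productivity. Neither the Year 2 plan nor the Return to Work plan covers it.

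**The case against.** The strongest reply is that the three-month rule is an openly stated simplification. Participants are only asked to keep track, and nothing shows that usable day counts for retirees exist. Productivity is also examined through work status and the Kaplan-Meier and log-rank return-to-work analysis, so the aim is not abandoned. Much of this stands, and it rules out several inferences a reader might draw:

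- *That the plan discards data it holds.* The documents show a request, not a data field or a completeness rate. This is why recorded days should not become the main analysis unconditionally.
- *That the procedures cannot be compared on productivity at all.* The fixed duration applies to retirees only, and return to work is analysed separately. That analysis, however, concerns work status and does not measure retirees' time to normal activity.
- *That total cost or the ICER is biased by a calculable amount or in a known direction.* Wage, retired share and recovery times are all missing, and step 3 shows that the sign can reverse.
- *That the societal total lacks an out-of-pocket term it needs.* Components A and B value hospital and professional care whoever pays, so adding copayments for that care would count it twice. What remains is the unanswered patient-perspective question.

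The reply does not remove the algebra in step 1 or supply the missing out-of-pocket method.

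**Conclusion.** The point holds in limited form. By construction, the retiree part of lost productivity cannot reveal a recovery-time difference between procedures and carries no recovery-time uncertainty into the ICER. This follows from the stated rule and needs no assumption. How much it matters to total cost or the ICER cannot be determined from the documents: it is zero if retirees recover alike after each procedure and of unknown size otherwise. The rule affects only the secondary economic analysis in United States patients; the SF-36 PCS analysis is untouched. The missing out-of-pocket analysis is a plain gap between Aim 2 and the methods, and the amounts involved are unknown. Both deserve correction because the relevant information was already requested from participants.

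**What to change.** **1. Retirees.** Add a pre-specified analysis that values each retiree's lost productivity at the stated 65% from participant-recorded days without usual activities. Name the form that holds the days and state the conversion to weeks (at 7 days per week, 91 days equals the 13 weeks now assumed). Use multiple imputation for missing days, and report completeness by procedure. Present the result beside the three-month assumption. Make it the main analysis only if the records exist and are adequately complete, with that criterion set before costs are compared. Otherwise, keep three months as the base value and vary it by procedure in the probabilistic analysis.

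**2. Out-of-pocket expense.** Compare it across the three procedures as a separate patient-perspective outcome, using the plan's own Gamma GLM with log link and its existing 10% rule for two-part modelling. Do not add to the societal total any spending already valued in components A or B.

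**Cost.** SAP wording and a modest amount of extra analysis, with no new data collection if the records were kept. The drawbacks are unknown completeness, reliance on a missing-at-random assumption, and the use of a day count as a proxy for elapsed recovery time.

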- The ICER will be calculated in a three-way extended dominance analysis, comparing each surgical treatment to the others. If a surgical procedure is both less costly and provides higher QALYs gained, that treatment will be dominant

over the others.

- A comparison of anterior and posterior approaches (namely, grouping the two posterior procedures) will be performed independently from the ICER model.
- Probabilistic analysis will be performed to account for sampling variation around ICER point estimates.
- Cost/QALY gained will be reported for each surgical treatment and for each approach.

d. Power Analysis.

Sample size for Specific Aim #1a (Ventral surgery is associated with superior SF-36 PCS outcome at one year compared to dorsal (fusion or laminoplasty surgery):

Sample size estimates were calculated based on analysis of covariance model with $\alpha = 0.05$ at 80% and 90% power using Power Analysis and Sample Size software (PASS 2008, NCSS, LLC. Kaysville, Utah). The primary endpoint is the SF-36 PCS. This component of the SF-36 is derived from the sums of scores of 21 items and thus exhibits distributional behavior commensurate with assumptions for parametric analysis. Our preliminary data suggest standard deviations for SF-36 PCS between 10 and 12 and correlations of baseline with one year SF-36 PCS between 0.6 and 0.7. *The following table describes the total sample size (2:3 ventral-dorsal randomization) required to detect a five point difference in SF-36 PCS one year post-surgery for various combinations of power, standard deviation and one year correlations under a fixed design.*

A minimum sample size of **137** patients provides at least 90% power (see Tables below):

Surgery (N)	Pre-op	Post-Op	Correlation between Pre- and Post-Op	Difference
Ventral (45)	35.5 ± 10.3	44.2 ± 11.7	0.64	+ 8.7 ± 8.2
Dorsal (70)	35.8 ± 11.3	39.8 ± 11.6	0.66	+ 4.0 ± 9.5
Dorsal Fusion (42)	35.0 ± 11.7	39.6 ± 12.4	0.65	+ 4.6 ± 10.0
Laminoplasty (28)	37.0 ± 10.9	40.1 ± 10.6	0.67	+ 3.1 ± 8.8
All patients (115)	35.7 ± 10.9	41.5 ± 11.8	0.64	+ 5.8 ± 9.7

Difference / SD	Correlation	80% Power / 5% Type I error (2-sided)			90% Power / 5% Type I error (2-sided)		
		N _{Ventral}	N _{Dorsal}	N	N _{Ventral}	N _{Dorsal}	N

5 / SD = 10	0.60	38	56	94	50	74	124
5 / SD = 10	0.65	40	59	99	53	78	131
5 / SD = 10	0.70	42	62	104	55	82	137

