The sample size will be inflated by 5% to accommodate multiple significance testing using an O'Brien-Fleming stopping boundary. Based on our preliminary data and pilot studies, withdrawal and loss-to-follow-up are not expected to be high. The sample size will be further inflated by 10% to accommodate attrition during the follow-up. Thus, 159 total patients will be recruited and randomized. **Ten high volume surgeons/ centers with the necessary expertise to permit patient randomization (16 randomized CSM cases/ site) have been selected to achieve the goal of enrolling 159 randomized patients over 18 months. An additional 91 nonrandomized patients will be enrolled into the study.**

Sample size for Specific Aim #1b (Compared to pre-operative baseline status, both ventral and dorsal surgery for CSM improve symptoms of spinal cord dysfunction at one year follow-up):

Using the sample size estimate for Specific Aim #1a and assuming ~10% attrition during follow-up, we expect to have 55 ventral surgery and 82 dorsal surgery patients (total = 137 patients) available for analysis. We will be able to detect changes from baseline pre-operative mJOA status as small as 2.0 points (clinically important difference) for both the ventral surgery cohort and the dorsal surgery cohorts at one year. Assumptions for this sample size analysis include Type I alpha = 0.025, power at 90%, and range of within-subject correlation of 0.60 to 0.70.

H. Economic Considerations

No subject will incur any additional cost for participating in this study. All of the pre- and post-operative CT, MRI, flexion-extension x-rays, and pre-operative sagittal balance films are considered standard of care. The post-operative sagittal balance films, which only randomized patients will receive, are not considered standard of care and will be billed directly to the research fund. All costs associated with the administration of the study will be assumed by the Patient-Centered Outcomes Research Institute (PCORI) and/or the Lahey Comparative Effectiveness Research Institute.

[figure not shown]
III. HUMAN SUBJECTS

A. Subject Population, Recruitment

Eligibility Criteria: Patients aged 45-80 years with CSM (≥ 2 levels of spinal cord compression from C3 to C7) presenting with ≥ 2 of the following symptoms/signs: clumsy hands, gait disturbance, hyperreflexia, up going toes, bladder dysfunction.

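### The cost model chooses covariates by an undefined baseline-imbalance rule, not by whether they predict cost, so confounding can remain in the partly non-randomized three-procedure comparison

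*Combined protocol and SAP*

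**What the plan says.** In section II.G.c, under Cost Analysis, the Statistical Analysis Plan paragraph specifies the model: "we will use generalized linear modeling (GLM) with Gamma distribution and a logarithmic link for cost". The covariate rule follows: "Any baseline patient characteristics found to be imbalanced between the cohorts will be adjusted for in the GLM". Nowhere do the documents list candidate characteristics, define imbalance (by p-value or by standardized difference), say when or by whom it is judged, or define the cohorts.

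The ICER subsection states the comparison: "The ICER will be calculated in a three-way extended dominance analysis, comparing each surgical treatment to the others". A separate anterior versus posterior comparison is also planned. The Power Analysis section describes only a "2:3 ventral-dorsal randomization". No random allocation between dorsal fusion and laminoplasty is described.

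The cost analysis is limited to US patients, with no number given. The plan does not say whether the 91 non-randomized patients enter it.

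Elsewhere the plan does fix covariates in advance: the primary SF-36 PCS model names baseline PCS and surgeon. The year-2 plan, by contrast, drops baseline adjustment because the groups looked similar.

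**The concern.** A covariate distorts a cost comparison when it differs between groups and also predicts cost. The rule looks only at the first condition, through an unstated filter. A strong cost predictor with a modest gap can be left out, and a variable unrelated to cost can be let in by chance.

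This matters most for dorsal fusion versus laminoplasty. As far as the documents show, that choice is made clinically, so patient differences there can be systematic. The plan's own costing points to likely predictors. Hospital costs use hospital-specific cost-to-charge ratios, yet site is not a patient characteristic and the rule need not reach it. Lost wages depend on occupation and are valued differently for retirees, so work status affects indirect cost by construction.

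At stake are the adjusted cost differences between procedures. If the year-2 judgement of similarity were repeated here, the cost model could contain no covariates at all.

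**Working it through.** **1. Sample size.** The Power Analysis section starts from 137 and inflates by 5% and then 10%: 137 × 1.05 × 1.10 = 158.2, rounded up to 159. This agrees with "Thus, 159 total patients will be recruited and randomized". The cost plan has no sample size of its own.

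**2. Group sizes (assumed).** A 2:3 split of 159 gives 159 × 2/5 = 63.6, so 64 ventral and 95 dorsal. The dorsal split is not planned. Using the pilot ratio of 42:28, 95 × 42/70 = 57 fusion and 38 laminoplasty. The US restriction can only lower these figures for the randomized set.

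**3. If imbalance means p < 0.05 (assumed).** For a true gap of d SD, the standard error of the observed gap is SE = √(1/n₁ + 1/n₂). The chance of a flag comes from the noncentral t distribution with noncentrality d/SE. For d = 0.3:

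| Contrast | n | SE | Flagged | Missed | Mean sample gap given a miss |
|---|---|---|---|---|---|
| Ventral vs fusion | 64/57 | 0.182 | 37% | 63% (62% by normal approximation) | 0.19 SD |
| Ventral vs laminoplasty | 64/38 | 0.205 | 31% | 69% | 0.20 SD |
| Fusion vs laminoplasty | 57/38 | 0.209 | 29% | 71% | 0.20 SD |

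The last column is the mean of a normal variable with mean d and standard deviation SE, truncated to the non-significant region.

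Detection depends strongly on d. For fusion versus laminoplasty it is 16%, 22%, 29%, 47% and 66% at d = 0.20, 0.25, 0.30, 0.40 and 0.50, and passes 50% at about 0.41. For ventral versus pooled dorsal (64/95) it passes 50% at about 0.32.

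**4. Bias left by a miss.** On the log link, an unadjusted covariate with slope b per SD and sample gap g multiplies the cost ratio by exp(g × b). Slopes of 0.15 to 0.30 are assumed.
- g = 0.19: exp(0.0285) − 1 = 2.9%; exp(0.057) − 1 = 5.9%.
- g = 0.20: exp(0.030) − 1 = 3.0%; exp(0.060) − 1 = 6.2%.

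**5. Bias averaged over all trials.** A Gamma log-link simulation was run with no true cost difference, 57 versus 38, one confounder and slope 0.30. Mean bias on the log scale, unadjusted and then under the p < 0.05 rule, was:
- d = 0.20: 0.062 to 0.037 (60% remains)
- d = 0.30: 0.091 to 0.044 (48% remains)
- d = 0.50: 0.154 to 0.033 (21% remains)

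**6. Several confounders.** With four confounders acting in the same direction (each 0.20 to 0.40 SD, slope 0.15, coefficient of variation 0.6; all assumed), the rule left 0.073 to 0.089 on the log scale, about 8 to 9% of cost. The false-positive rate was 8 to 10%. Always adjusting left at most 0.009, with 5.4 to 6.0% false positives.

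**7. If imbalance means an observed standardized difference above 0.1.** A truly balanced covariate is flagged with probability 2 × [1 − Φ(0.1/SE)]: 54% at 64/95, 58% at 64/57 and 63% at 57/38. The rule then over-includes. Even with a 5% test, the chance that at least one of 10 independent balanced covariates is flagged is 1 − 0.95¹⁰ = 40%.

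**The case against.** The strongest reply is that the rule can work. Selection uses baseline data and not cost results, and large gaps are mostly caught. This is also a secondary economic analysis. All of that stands. It does not supply the missing criterion, and it does not make observed imbalance a good guide to which variables matter for cost.

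Four stronger readings are tempting and are not supported:

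- *The rule misses most real confounding.* This needs two things the documents do not state: a 5% test, and gaps below about 0.3 to 0.4 SD. With a 0.1 threshold the fault reverses.
- *Each miss leaves 5 to 9% bias.* That puts the full 0.3 SD gap into the formula (4.6% and 9.4% for slopes 0.15 and 0.30). Samples that escape the test have smaller gaps, so 3 to 6% is the right range.
- *Ventral versus dorsal is confounded.* If it is analysed as randomized, imbalance is chance. Systematic confounding applies to fusion versus laminoplasty, to as-treated groups, and to non-randomized patients if they are included. With all 250 patients (assumed 100/150 and 90/60), detection of a 0.3 SD gap rises to 64% for ventral versus dorsal but only 43% for fusion versus laminoplasty.
- *The selection step itself makes the confidence intervals invalid.* This is not shown. With one truly balanced covariate (64/95, slope 0.30), the rule gave 4.3% false positives. The excess in the four-confounder runs reflects residual confounding.

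The documents also do not say whether the ICER uses model-adjusted or raw costs, so an effect on the ICER is possible but not established.

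**Conclusion.** The point holds as a fault of method. The plan chooses cost covariates by an undefined imbalance rule that ignores their relation to cost, in a comparison that is only partly randomized. Under a 5% test and the assumed group sizes, a 0.3 SD gap is missed in about 62 to 71% of trials, and a miss leaves about 3 to 6% bias in the cost ratio per covariate. Several such covariates can add up. Under a 0.1 threshold, over half of balanced covariates enter needlessly. Neither outcome is desirable, and the plan does not say which applies. The group sizes, the slopes and the meaning of imbalance are all assumptions. The absence of a list and of a criterion is not. For ventral versus dorsal analysed as randomized, what is lost is mainly precision. The change should be made, but the SF-36 PCS primary analysis is unaffected.

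**What to change.** Replace the imbalance rule with a short list of cost predictors, fixed before the cost data are examined and adjusted for whatever the observed balance. Age, baseline EQ-5D utility and baseline mJOA are natural choices. The data-sheet list shows EQ-5D and mJOA before surgery, and age is an eligibility criterion. Sex, anesthesia class, number of compressed levels and pre-operative work status should be added only where the baseline and surgeon forms record them. The listed return-to-work sheet starts at 1 month, and anesthesia class and compressed levels appear in the text only as eligibility thresholds.

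Handle site as a random effect or by clustering. Clustering corrects standard errors but does not remove cost differences between sites, so a random effect is preferable if procedure use varies by site. State the analysis population, including whether the 91 non-randomized patients enter. Keep any imbalance-based adjustment as a sensitivity analysis, with its threshold defined.

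The cost is plan wording, and no new data if the forms hold these items. The real price is degrees of freedom. Ten centers as fixed effects use 9, and seven further covariates bring the total to at least 16, against about 38 laminoplasty patients or fewer. The list must therefore stay short, and site should not be a fixed factor.
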